11.2 Datasets to be analyzed

Data from all subjects who receive any study drug will be included in the determination of the maximum tolerated dose, unless they withdrew from the study before completing 1 cycle of therapy for reasons other than tolerability/toxicity.

Data from all subjects who receive any study drug will be included in the safety analyses. Subjects who enter the study but do not take any of the study drug(s), and have had this confirmed, will not be evaluated for safety.

Data from all subjects who received at least 1 cycles of therapy will be used in the analysis of drug efficacy.

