6.4 Drug Administration

6.4.1 Treatment assignments

This is a Phase I non-randomized study. Eligible patients will be allocated to treatment in the order in which they sign the informed consent and that all documentation needed to confirm eligibility has been completed. A maximum of 30 subjects will be enrolled and treated with single agent pomalidomide. Starting at dose level 1 in Schedule A, the study will enroll patients in cohorts of 3, following a standard 3 +3 statistical design. (see Section 11.0).

Definition of Dose Limiting Toxicity (DLT):

Toxicity will be evaluated according to the NCI CTCAE version 4.0, (see Appendix E)

1) Non-hematologic dose limiting toxicity (DLT) is defined as any grade ≥ 3 non-hematological toxicity occurring during the first 28 days (first cycle) of treatment, with the specific exception of:

- Isolated Grade 3 elevation of liver function tests (LFTs) without associated clinical symptoms, lasting for ≤ 7 days in duration.
- Isolated Grade 3 elevation of amylase without associated clinical symptoms
- Grade 3 hypocalcemia, hypokalemia, hypomagnesemia, hyponatremia, or hypophosphatemia which responds to medical intervention.

2) Hematological dose limiting toxicity is defined as Grade ≥ 3 neutropenia with fever ≥ 38.5 , Grade 4 neutropenia lasting for ≥ 7 days in duration, or any Grade 4 anemia or thrombocytopenia occurring during the first 28 days (first cycle) of treatment.

Definition of Maximum Tolerated Dose (MTD): MTD is defined as the highest dose level in which 6 patients have been treated with less than 2 instances of DLT.

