If a dose of pomalidomide is missed, it should be taken as soon as possible on the same day. If it is missed for the entire day, it should not be made up, rather it should be taken at the next scheduled time point.

Patients who take more than the prescribed dose of pomalidomide should be instructed to seek emergency medical care if needed and contact study staff immediately.

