6.4.5 Dose Modification or Interruption

Pomalidomide Dose Reductions

Dose reduction(s) will be allowed for any subject who develops a DLT during Cycle 1 or beyond Cycle 1 who develops a toxicity that, in the opinion of the Investigator, requires a dose-reduction.

For treatment interruptions during a cycle, the (28- or 21-day) schedule of each cycle will continue to be followed. Missed doses of pomalidomide are not made up.

For treatment interruptions that delay the scheduled start of a new cycle, when toxicity has resolved as required to allow the start of a new cycle (Section 6.5), the restart day of therapy becomes Day 1 of the next cycle.

The following table provides the dose reduction sequence for pomalidomide:

Table 2: Schedule of Pomalidomide Dose Reduction

	If the DLT/Toxicity occurred or recurred at --- (mg/dose/d 1-28 or d 1-21 depending on Schedule):	Reduce dose to --- (mg/dose/d 1-28 or d 1-21 depending on Schedule):
Pomalidomide	4	3
	3	2
	2	1
	1	0.5

Dosing interruptions and reductions are not permitted during Cycle 1 unless the subject experiences a DLT. Dose interruptions and reductions are permitted beyond Cycle 2. Examples of possible reasons for and extent of dose modification management are outlined in Table 3. The events listed are not all-inclusive and are based on observations pooled from studies with all compounds in the IMiD® class of drugs. Therefore, these events may occur but are not necessarily expected. The investigator may choose to modify pomalidomide dosing further downward or discontinue pomalidomide treatment for any adverse event.

Study drug may be held (up to 21 days) and subsequent dose reductions made as outlined in Table 3. If study drug needs to be held > 21 days, the patient is to be taken off study. Once a dose has been reduced, it cannot be re-escalated.

At the discretion of the Investigator, the use of G-CSF will be permitted to manage neutropenic fever or a Grade 4 neutropenia.

Table 3: Pomalidomide Dosage Modifications for cycles ≥ 2

Common Terminology Criteria (CTCAE) Version 4.0	Adverse Event	Dose Change for Pomalidomide
Allergy/Immunology	Allergic reaction/ hypersensitivity (including drug fever) Grade 2	Hold study drug until resolved to \leq Grade 1; Decrease dose by 1 dose level
Allergy/Immunology	Allergic reaction/ hypersensitivity (including drug fever) Grade 3 or 4	Discontinue Study Drug

Common Terminology Criteria (CTCAE) Version 4.0	Adverse Event	Dose Change for Pomalidomide

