11.1 Overview

This is a Phase I study of single agent pomalidomide in patients with symptomatic Waldenström macroglobulinemia whose disease has relapsed and/or is refractory to at least one prior line of therapy.

The objectives of this phase I study are to assess the safety profile of pomalidomide in patients with relapsed Waldenström macroglobulinemia and to determine the maximum tolerated dose (MTD) of pomalidomide in this patient population.

There are four predefined dose levels (1, 2, 3, and 4) for pomalidomide. The study also includes two alternative dosing schedules (A and B). With schedule A, patients will be treated with the study drug for 28 days within each cycle. If the MTD is exceeded at dose level 1 of Schedule A, Schedule B will be explored. With schedule B, patients will be treated for 21 days within each cycle.

Non-hematologic dose limiting toxicity (DLT) is defined as any grade ≥ 3 non-hematological toxicity occurring during the first cycle (28 days on dosing schedule A and 21 days on dosing schedule B) of treatment, with the specific exception of:

- Isolated Grade 3 elevation of liver function tests (LFTs) without associated clinical symptoms, lasting for ≤ 7 days in duration.
- Isolated Grade 3 elevation of amylase without associated clinical symptoms
- Grade 3 hypocalcemia, hypokalemia, hypomagnesemia, hyponatremia, or hypophosphatemia which responds to medical intervention.

Hematological dose limiting toxicity is defined as Grade ≥ 4 neutropenia lasting for ≥ 7 days in duration, any Grade 4 anemia or thrombocytopenia, or any Grade 5 hematologic toxicity occurring during the first cycle (28 days on dosing schedule A and 21 days on dosing schedule B) of treatment.

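### Section 11.2 can drop a patient with a DLT from the MTD determination, and it counts barely exposed patients and low-grade early stoppers as DLT-free

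*Combined protocol and SAP*

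**What the plan says.** Section 11.2 opens with the set for the MTD: "Data from all subjects who receive any study drug will be included in the determination of the maximum tolerated dose". A single exception then removes some early leavers from that set: "unless they withdrew from the study before completing 1 cycle of therapy for reasons other than tolerability/toxicity". There is no minimum number of doses, no definition of a DLT-evaluable patient and no replacement rule, there or elsewhere.

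A DLT is a yes/no outcome with a floor at Grade 3. Section 6.4.1 defines the non-hematologic part as "any grade ≥ 3 non-hematological toxicity occurring during the first 28 days (first cycle) of treatment", with listed exceptions. Section 11.1 has the same grade threshold but sets the first cycle at 28 days on Schedule A and 21 days on Schedule B. The hematologic parts differ between the two sections: 6.4.1 includes febrile neutropenia ("Hematological dose limiting toxicity is defined as Grade ≥ 3 neutropenia with fever"), while 11.1 leaves it out and ends with "any Grade 4 anemia or thrombocytopenia, or any Grade 5 hematologic toxicity occurring during the first cycle". Neither admits a Grade 1-2 event, and neither makes stopping for intolerance a DLT.

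The algorithm in Section 11.1 escalates on 0 of 3, expands on 1 of 3, and escalates on 1 of 6. It acts whenever a second DLT is seen at a level. The MTD is the highest level with six treated patients and fewer than two DLTs, so its denominator is patients treated, not patients evaluable.

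On exposure, Section 6.4.5 does not permit interruptions or reductions in Cycle 1 without a DLT. Section 6.4.2 says of a missed dose: "If it is missed for the entire day, it should not be made up". Section 6.7 lists consent withdrawal, loss to follow-up and major protocol violation among the reasons for ending treatment, as well as adverse events in the investigator's judgement.

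**The concern.** A 3+3 design decides on three or six patients, so the scoring of one patient can change the outcome. Two features of the rule misclassify patients in the same direction.

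**A DLT can be excluded.** The exclusion turns on the reason for withdrawal and makes no exception for a DLT already observed. A patient with a DLT on day 10 who withdraws consent on day 20 for an unrelated reason falls outside the MTD set. The algorithm in Section 11.1 would already have counted that event. The two sections then disagree on the primary endpoint, and nothing says which governs.

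**Uninformative patients count as tolerating the dose.** A patient who stays on study after a handful of doses, or who stops in Cycle 1 for Grade 1-2 intolerance, is in the set and meets no DLT criterion. With a yes/no outcome, that patient is a DLT-free member of the denominator.

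At stake is an MTD set too high. The six additional patients would then be treated at that dose.

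**Working it through.** **The plan's own figure.** Section 11.6 gives up to 30 patients for dose finding. Six at level 1 of Schedule A plus four levels of six on Schedule B is 6 + 4 × 6 = 30, which reproduces it. It contains no allowance for replacements.

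**Formula.** From the algorithm in Section 11.1, a level passes on 0 of 3, or on 1 of 3 followed by 0 of 3. With per-patient DLT probability p:

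pass(p) = (1−p)³ + 3p(1−p)² × (1−p)³ = (1−p)³ + 3p(1−p)⁵

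All values of p, f and q below are assumptions, because the documents give none.

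**1. DLT patients dropped.** A share f of DLT patients leaves in Cycle 1 for another reason, is excluded and is replaced. Replacement is also an assumption, as the plan has no such rule. The effective rate is p′ = p(1−f)/(1−pf). With p = 0.33, pass(0.33) = 0.301 + 0.134 = 0.434.

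| f | p′ | pass(p′) |
|---|---|---|
| 0 | 0.330 | 0.434 |
| 5% | 0.3135/0.9835 = 0.319 | 0.456 |
| 10% | 0.297/0.967 = 0.307 | 0.480 |
| 20% | 0.264/0.934 = 0.283 | 0.530 |

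**2. Low-grade early stoppers.** Of all patients at a level, 25% have a DLT and a further share q stops in Cycle 1 for Grade 1-2 intolerance. As written, the stoppers are DLT-free, so the rate stays 0.25 and pass(0.25) = 0.422 + 0.178 = 0.600. If they are replaced, the rate among evaluable patients is 0.25/(1−q).

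| q | 0.25/(1−q) | pass, stoppers replaced | pass, as written |
|---|---|---|---|
| 5% | 0.263 | 0.57 | 0.600 |
| 10% | 0.278 | 0.54 | 0.600 |
| 15% | 0.294 | 0.51 | 0.600 |

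**3. Under-exposed patients, limiting case.** Suppose a share q takes too little drug to have any chance of a DLT, and fully exposed patients have a 30% rate. The scored rate is 0.30(1−q). The pass probability is 0.525, 0.557 and 0.622 for q = 5, 10 and 20%, against 0.494 if those patients are replaced. This is an upper bound for each q, since some exposure carries some risk.

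**One patient.** Take a cohort with 1 DLT in 3. If that patient is excluded and the replacement is DLT-free, the cohort reads 0 of 3 and the dose escalates without expansion to six.

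**The case against.** Several points on the other side stand, and they limit the size.

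- **The algorithm would probably count an observed DLT in real time.** Section 11.1 acts on DLTs as they occur, and the event stays in the safety set of Sections 11.2 and 11.3. A reader might infer that DLTs will simply be lost from the trial. The documents do not support that. They support a conflict between the algorithm and the analysis set.
- **The dropped-DLT case is narrow.** It needs a DLT and then withdrawal from the study, for an unrelated reason, within the rest of Cycle 1. Stopping drug alone may not qualify, since Section 6.8 keeps such patients in follow-up. But the more narrowly withdrawal is read, the more patients who stop drug early for unrelated reasons stay in the set as DLT-free.
- **Low exposure is restrained.** Section 6.4.5 bars Cycle 1 interruptions without a DLT, and Section 6.5.1 reconciles diaries with capsule counts. A reader might cite "The investigator may choose to modify pomalidomide dosing further downward or discontinue pomalidomide treatment for any adverse event" as overriding that bar. The sentence closes the paragraph that introduces Table 3, which is for cycles 2 and later, so its reach into Cycle 1 is doubtful. The point does not need it: Section 6.7 allows treatment to end for adverse events or withdrawn consent at any time. The bar governs dosing and does not say who is evaluable.
- **Ignoring Grade 1-2 events is a choice made in the DLT definition.** Section 11.2 says only that these patients are included; that they are DLT-free is an inference, though a binary outcome leaves no other score. A reader might go further and count low-grade stops as DLTs, which at a 25% DLT rate would cut the pass probability from 60% to 49, 40 or 31% for 5, 10 or 15% stops. That contrast measures a changed DLT definition, which the documents give no ground for. The fair comparison is with replacement: 57, 54 or 51%.

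**Conclusion.** The point holds as a conflict and a gap in the rule for the primary endpoint. Section 11.2 as worded can exclude a patient with a Cycle 1 DLT whom Section 11.1 would count. It also admits barely exposed patients and low-grade early stoppers as DLT-free. Both effects favour escalation.

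The size is moderate: 2 to 10 percentage points on the pass probability of a true 33% dose for dropped DLTs at 5-20%, and 3 to 9 points at a 25% DLT rate for low-grade stoppers at 5-15%. These figures rest on assumed rates, independent patients and one-for-one replacement. The direction does not depend on the particular rates chosen. The change is worth making before the first cohort, because it concerns the primary endpoint and is cheap.

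**What to change.** Rewrite the first paragraph of Section 11.2 so that the DLT-evaluable set is:

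- (a) every patient with a DLT in the DLT window, whatever the later reason for leaving; plus
- (b) DLT-free patients who completed the window and took at least a share of planned Cycle 1 doses, fixed before the first cohort.

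DLT-free patients who do not meet (b), including those who stop for lower-grade intolerance, are not counted as DLT-free. They are listed by dose level with the reason, and replaced. Make the algorithm and the MTD definition in Sections 6.4.1 and 11.1 refer to this set instead of to patients treated. This point needs no change to the grade criteria for a DLT. The window on Schedule B must be reconciled, since Section 6.4.1 says 28 days and Section 11.1 says 21.

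**Cost.** Part (a) needs no extra patients or data. Part (b) uses the diaries and capsule counts of Section 6.5.1. At an assumed 5-10% non-evaluable rate, replacements number about 24 × 0.05 = 1.2 to 30 × 0.10 = 3. They must be reconciled with the cap of 30 in Section 6.4.1, which the worst cases already use up: 24 + 6 = 30 on Schedule A including the six extra patients at the MTD, and 6 + 24 = 30 on the Schedule B path before those six (36 with them). State whether replacements count against the cap.

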Dose level 1	1 mg orally on days 1-28	1 mg orally on days 1-21
Dose level 2	2 mg orally on days 1-28	2 mg orally on days 1-21
Dose level 3	3 mg orally on days 1-28	3 mg orally on days 1-21
Dose level 4	4 mg orally on days 1-28	4 mg orally on days 1-21

Dose escalation will continue in 1 mg increments until the MTD is reached. Once the MTD has been determined, an additional 6 patients will be treated at this dose level.

Patients will continue receiving treatment until either disease progression or unacceptable toxicity develops.

STUDY ENDPOINTS

- **Primary:** 1) The primary endpoint is the maximum tolerated dose (MTD) of pomalidomide in patients with symptomatic Waldenström macroglobulinemia (WM) whose disease has relapsed/and or is refractory to at least 1 prior line of therapy. Tolerability of a given dose will be assessed after every 3 patients have been enrolled, until the maximum tolerated dose has been defined or, in the absence of dose limiting toxicities, the highest planned dose level is determined to have an acceptable toxicity profile.
- **Secondary:** 1)The safety and toxicity profile of pomalidomide will be evaluated after all patients to be enrolled have completed 1 cycle of therapy; patients who received at least 1 dose of pomalidomide will be eligible for evaluation.
2) The efficacy of pomalidomide will be measured as best response to therapy. For each patient, this will be determined at the completion of their course of therapy. The collective data will be summed at study completion. Patients will be considered evaluable if they have completed at least 1 cycle of therapy.

STUDY DURATION: 3 years (expected)	TOTAL SAMPLE SIZE: maximum of 30
DOSING REGIMEN(S): Schedule A: Dose level 1 : 1 mg orally on days 1-28 Dose level 2 : 2 mg orally on days 1-28 Dose level 3 : 3 mg orally on days 1-28 Dose level 4 : 4 mg orally on days 1-28 Schedule B: Dose level 1: 1 mg orally on days 1-21 Dose level 2: 2 mg orally on days 1-21 Dose level 3: 3 mg orally on days 1-21 Dose level 4: 4 mg orally on days 1-21	STUDY DRUG SUPPLIES: Celgene Corporation will supply pomalidomide as 0.5 mg, 1.0 mg and 2.0 mg

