⁴Electrolytes, BUN, Creatinine, Calcium, Magnesium, Phosphorous, Albumin, Total Bilirubin (fractionated, if elevated), ALT, AST, Alkaline Phosphatase, Beta 2 microglobulin; A Thyroid Stimulating Hormone (TSH) level is to be drawn at Screening, and as clinically indicated. T3 and T4 levels may be assessed as clinically indicated. Cryocrit, Cold Agglutinin Titer and serum viscosity are to be drawn at screening; if abnormal on screening, they are to be repeated at treatment discontinuation (within 5 days prior to Day 1 of each cycle).

⁵Indicated for females of childbearing potential. A female of childbearing potential (FCBP) is a sexually mature female who: 1) has not undergone a hysterectomy or bilateral oophorectomy; or 2) has not been naturally postmenopausal for at least 24 consecutive months (i.e., has had menses at any time in the preceding 24 consecutive months).

⁶Pregnancy tests (either urine or serum β HCG) must occur 10 – 14 days prior, and again within 24 hours prior to initiation of pomalidomide. FCBP with regular or no menstruation must have a pregnancy test weekly for the first 4 weeks and then every 28 days while on therapy (including breaks in therapy); at discontinuation of pomalidomide and at Day 28 post the last dose of pomalidomide. Females with irregular menstruation must have a pregnancy test weekly for the first 4 weeks and then every 14 days while on therapy (including breaks in therapy), at discontinuation of pomalidomide and at Day 14 and Day 28 post the last dose of pomalidomide (see Appendix A: Risks of Fetal Exposure, Pregnancy Testing Guidelines and Acceptable Birth Control Methods).

⁷All patients must be counseled about pregnancy precautions, risks of fetal exposure and other risks. The counseling must be done on Day 1 of each cycle (or at a minimum of every 28 days) and at drug discontinuation. See Appendix A: Pomalidomide Risks of Fetal Exposure, Pregnancy Testing Guidelines and Acceptable Birth Control Methods and Appendix B: Pomalidomide Education and Counseling Guidance Document

⁸If these CT/MRI assessments show no adenopathy or hepatosplenomegaly at screening, they will only be repeated at discontinuation of study drug. These imaging studies should be performed within 7 days prior to Day 1 of each odd cycle.

⁹All PRs and CRs must be confirmed by repeat scans no less than 6 weeks after the criteria for response are first met. The first response assessment will take place at completion of cycle 2.

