7.6 Adverse event updates/IND safety reports

Celgene shall notify the Investigator via an IND Safety Report of the following information:

- Any AE associated with the use of study drug in this study or in other studies that is both serious and unexpected.
- Any finding from tests in laboratory animals that suggests a significant risk for human subjects including reports of mutagenicity, teratogenicity, or carcinogenicity.

The Investigator shall notify his/her IRB/EC promptly of these new serious and unexpected AE(s) or significant risks to subjects.

The Investigator must keep copies of all AE information, including correspondence with Celgene and the IRB/EC, on file (see Section 12.4 for records retention information).

8 Response Criteria²⁵

Baseline disease assessments must occur within \leq 28 days of study drug administration.

Response assessments will be performed after each cycle of pomalidomide has been administered. Response will be assessed by either the principal investigator or a sub-investigator, and then documented in the UTMDACC protocol data management system (PDMS). Because of the IgM flare phenomenon²⁶, progressive disease cannot be confirmed until the response assessment performed after the second cycle of pomalidomide, has been reviewed. All partial and complete responses must be confirmed with a second efficacy assessment, performed at least 6 weeks later.

Definitions of response:

1. **Complete response (CR):** categorized by the disappearance of serum and urine monoclonal protein determined by immunofixation, absence of malignant cells in the bone marrow determined by histologic evaluation, resolution of adenopathy/organomegaly (confirmed by computed tomography [CT] scan) and no signs or symptoms attributable to WM. Reconfirmation of the CR status is required \geq 6 weeks later with a second immunofixation.
2. **Partial response (PR):** categorized by \geq 50% reduction of serum monoclonal IgM concentration determined by protein electrophoresis, \geq 50% decrease in

adenopathy/organomegaly on physical examination or on CT scan and no new symptoms or signs of active disease.

3. **Minor response (MR):** categorized by a $\geq 25\%$ but $<50\%$ reduction of serum monoclonal IgM concentration determined by protein electrophoresis and no new symptoms or signs of active disease.

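### The efficacy set drops treated patients who stop in Cycle 1, so a confirmed PR/CR rate calculated on it can only move upward, by a modest amount

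*Combined protocol and SAP*

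**What the plan says.** Efficacy is a secondary objective, measured as each patient's best response during therapy and collected over all patients at study end (synopsis; Section 5.2.2). No hypothesis, response rate or efficacy decision rule is given.

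The efficacy set is described in three places. Section 11.2: "Data from all subjects who received at least 1 cycles of therapy will be used in the analysis of drug efficacy". The synopsis and Section 5.2.2: "Patients will be considered evaluable if they have completed at least 1 cycle of therapy". One wording turns on cycles *received*, the other on cycles *completed*.

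The other two sets treat early stoppers differently. For safety, Section 11.2 says: "Data from all subjects who receive any study drug will be included in the safety analyses". For the MTD, it drops a patient who withdraws before the end of Cycle 1 only if the reason was something other than tolerability or toxicity.

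On response, Section 8 says: "All partial and complete responses must be confirmed with a second efficacy assessment, performed at least 6 weeks later". Minor response carries no such requirement. Section 8 also says: "Response assessments will be performed after each cycle of pomalidomide has been administered". Footnote 9 of the Section 2 schedule says: "The first response assessment will take place at completion of cycle 2".

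**The concern.** A patient who takes pomalidomide and stops in Cycle 1, for example because of an adverse event, death or withdrawn consent (Section 6.7), counts for safety but not for efficacy. No all-treated response analysis is specified, and no rule counts such a patient as a non-responder.

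If the excluded patients cannot be confirmed responders, leaving them out shrinks the denominator and never the numerator. When the stop is for toxicity, the exclusion is also tied to tolerability, which is what this trial studies. Section 10.2 asks the Data Monitoring Committee to weigh risk against benefit. The risk side would then describe all treated patients and the benefit side a selected subset.

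**Working it through.** **Inputs from the documents**
- N = 12 at the MTD: 6 patients required by the MTD definition (Section 6.4.1) plus 6 additional (Section 6.4.2).
- N = 30, the stated maximum. Section 11.6 is reproduced by 6 on Schedule A level 1 plus 4 levels × 6 on Schedule B = 30.
- Confirmation at least 6 weeks = 42 days after the criteria are first met (Section 2, footnotes 9 and 14; Section 8).
- Last scheduled visit: 30 days ± 1 week after the last dose (Section 2, footnote 11; Section 6.8).

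**Inputs assumed**
- The plan gives no response rate to reproduce. I use r = 3 of 12 (25%, the single-agent thalidomide rate cited in Section 4.1) and r = 8 of 30, as illustrations only.
- d, the number stopping in Cycle 1, is not in the documents and is varied.

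**Step 1: can a Cycle 1 stopper be a confirmed PR/CR?** Response laboratory tests are tied to Day 1 of each cycle (Section 2, footnote 13). This patient's first scheduled post-baseline response evaluation is therefore at discontinuation, taken to be on or after the last dose. The last scheduled visit is at most 30 + 7 = 37 days after the last dose. Even if response were assessed there, 37 < 42. Later contacts collect only subsequent treatment and survival (Section 6.8). So, on the scheduled visits, the answer is no.

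**Step 2: effect on the rate.** The plan's set gives r/(N-d) and all treated patients give r/N. The ratio is N/(N-d), which exceeds 1 whenever d ≥ 1. The rate itself rises when r ≥ 1 as well.

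| N | r | d | Rate | Exact 95% CI | N/(N-d) |
|---|---|---|---|---|---|
| 12 | 3 | 0 | 25.0% | 5.5–57.2% | 1.00 |
| 12 | 3 | 1 | 27.3% | 6.0–61.0% | 1.09 |
| 12 | 3 | 2 | 30.0% | 6.7–65.2% | 1.20 |
| 30 | 8 | 0 | 26.7% | 12.3–45.9% | 1.00 |
| 30 | 8 | 1 | 27.6% | 12.7–47.2% | 1.03 |
| 30 | 8 | 2 | 28.6% | 13.2–48.7% | 1.07 |
| 30 | 8 | 3 | 29.6% | 13.8–50.2% | 1.11 |

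With no responders the estimate stays at 0%. Only the upper limit moves, from 26.5% (0/12) to 28.5% (0/11).

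**Step 3: how likely is at least one early stopper?** With 3 of 12 fixed as confirmed responders, only the other 9 can stop in Cycle 1, so P(d ≥ 1) = 1 - (1-p)^9. For an assumed p of 2%, 5% or 10% this is 17%, 37% or 61%. The average reported rate, the mean of 3/(12-d), is 25.4%, 26.1% or 27.2%.

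**Step 4: if minor response counts.** It needs no confirmation, so an early stopper could hold it. Suppose 4 of 12 respond and one of the four is an early stopper in minor response. All treated gives 4/12 = 33.3%, and the plan's set gives 3/11 = 27.3%. The direction reverses.

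**Step 5: do *received* and *completed* select the same patients?** Not always.
- Doses missed for a whole day are not made up (Section 6.4.2).
- Drug is stopped while a missed period or abnormal pregnancy test is evaluated (Appendix A).
- On Schedule B, a patient who leaves on days 22–28 has had all 21 dosing days but has not finished the 28-day cycle of Section 6.4.2. Section 11.1 gives that schedule's first cycle as 21 days.
- After a DLT, doses may be held while the cycle calendar continues (Section 6.4.5).

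**The case against.** The strongest reply is that this is a pre-specified restriction on a secondary, untested endpoint in at most 30 patients, and that a shift of 2.3 points is lost in an interval of 5.5% to 57.2%. A reader given the safety-set N could recompute the rate. There is also a possible rationale: Section 8 assesses response after each cycle, and because of IgM flare "progressive disease cannot be confirmed until the response assessment performed after the second cycle of pomalidomide, has been reviewed". A one-cycle minimum matches the first assessment under Section 8. All of this stands as to size. It does not justify a shift that is avoidable and, for a confirmed PR/CR rate, goes only one way.

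Two further objections limit the point. First, the plan names no response rate, so the claim concerns any confirmed PR/CR rate calculated on this set. Second, the 42 days run from when the criteria are first met, and Section 2 allows unscheduled visits whose data are recorded, so an early response could in principle be confirmed off schedule. An all-treated set would credit such a patient.

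Several stronger readings are tempting but not supported:
- *A Cycle 1 DLT removes the patient from efficacy.* It does not by itself, because Section 6.4.5 allows dose reduction after a DLT.
- *Toxicity is hidden or the MTD is biased.* Patients who stop for toxicity stay in both the safety and the MTD sets.
- *The received/completed wording matters only after a DLT.* A reader might infer this from "Dosing interruptions and reductions are not permitted during Cycle 1 unless the subject experiences a DLT", but the first three cases in Step 5 involve no DLT.
- *The chance of an early stopper is 22%, 46% or 72%.* That draws stoppers from all 12 patients, although 3 have already been fixed as confirmed responders.

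**Conclusion.** The point holds as a modest improvement. The one-cycle minimum leaves out treated patients who, on the scheduled visits, cannot be confirmed responders. A confirmed PR/CR rate on that set therefore exceeds the all-treated rate by the factor N/(N-d) whenever at least one patient stops in Cycle 1 and at least one confirmed response is seen. In the illustration at the MTD this is 2.3 points for one stopper and 5.0 for two.

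This rests on three assumptions: the discontinuation evaluation falls on or after the last dose, no response is confirmed at unscheduled visits, and minor response is not counted. The number of early stoppers is unknown, and with none the two sets give the same rate. The documents do not support saying that the trial's response rate will be overstated, since the plan defines no such rate and the direction can reverse if minor response is included.

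**What to change.** In the synopsis, Section 5.2.2 and Section 11.2:
- Make the main efficacy set all patients who received any pomalidomide, which is the existing safety set.
- Count PR and CR only if confirmed, and count patients with no post-baseline response assessment as non-responders.
- Keep the at-least-one-cycle set as supportive, with a single definition of a completed cycle. It should cover any held, missed or truncated Cycle 1 dosing, including Schedule B patients who leave on days 22–28, and not only holds after a DLT.

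Section 2 footnote 9 and Section 8 give different times for the first response assessment and must be reconciled, because this decides whether an early stopper has an assessment at all.

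The cost is wording in those three places plus the reconciliation of Sections 2 and 8. No new patients or data are needed. The reported confirmed PR/CR rate may come out slightly lower.
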